Statistical Analysis Plan

Investigating the Effectiveness of an Entertainment Education Short Film for Internalized HIV

Stigma Reduction, Intimate Partner Status Disclosure Intentions, and Antiretroviral Medical

Adherence Intentions: A Randomized Controlled Trial Among Black Women Living with HIV

in the Southern U.S.

ClinicalTrials.Gov Identifier: NCT03898063

February 15, 2021

Introduction: Purpose of the Statistical Analysis Plan (SAP)

The purpose of this Statistical Analysis Plan (SAP) is to detail the study objectives, study hypotheses and research questions, as well as the primary outcome measures and data analyses.

Study Overview

This randomized controlled trial was conducted among Black women living with HIV in the Southern U.S. between the ages of 18 and 50. The study examined the efficacy of a short entertainment education (EE) narrative in comparison to a standard brochure for primarily improving the following: HIV status disclosure intentions, internalized HIV-related stigma, and antiretroviral medical adherence. Once consented, all participants completed a pre-test survey. Upon completing the pre-test, using the randomization feature in Qualtrics, participants were randomly assigned to one of two study arms: 1) EE narrative or 2) Brochure. After viewing the EE stimulus or the brochure, participants immediately completed a post-test survey. The primary aim of the study is listed below.

Aim 1. To investigate the effectiveness of an EE intervention for decreasing internalized HIV-stigma and increasing HIV status disclosure intentions and medical adherence intentions among Black women living with HIV in the Southern U.S.

The hypotheses guiding this research study included the following:

H_{1a-c}: Participants in the EE condition will report: a) lower levels of internalized stigma; b) higher levels of disclosure intentions; c) higher levels of medical adherence intentions.

Data Collection Plan

Participants will be recruited via two primary methods. Firstly, Facebook advertisements will be deployed to recruit participants who meet the inclusion criteria. Secondly, participants will be recruited via a Qualtrics panel.

Statistical Methods

An Analysis of Covariance (ANCOVA) will be used to control for the influence of age on the relationships of interest. This analysis will determine if there is a statistically significant difference between the treatment arm (90 DAYS film) and the control arm (Brochure) on the following primary variables: internalized stigma, intentions to disclose, and intentions for medical adherence. The analyses will be conducted using SPSS version 24.

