We propose a randomized clinical trial (RCT) with a pre and post questionnaire assessing two conditions: (1) standard-of-care brochure (control condition) and (2) the EE film (treatment condition). For those currently enrolled in the study (N=3) outcomes will be assessed with two post questionnaires, the first to assess intentions immediately after exposure to the study conditions and the second to assess lasting effects of the intervention on behavior one month later. The second questionnaire will primarily evaluate participants' disclosure attitudes and beliefs, intimate partner disclosure intentions, medical adherence intentions, disclosure behavior, adherence behavior and reported internalized stigma. However, for newly enrolled participants only one post questionnaire will be assigned. Therefore, after completing the pre-test, intervention, and immediate post-test, they will not complete a follow up questionnaire. Thus, instead of participating in two waves of data collection, newly enrolled participants will only participate in one wave of data collection.

Prior to beginning the study, researchers will conduct a manipulation check for the PSA to ensure it is yielding the intended effects. The pre-test of the PSA will be conducted with 15-30 research participants. For the manipulation check, participants will provide verbal consent in place of signed consent. Therefore, completing the pre and post-test questionnaires will serve as their agreement to study participation. Participants will either be randomly assigned to view the PSA or to the control condition in which no stimulus will be used. Study conditions will

Version 10.5.2018 Page 2 of 11

be randomly assigned based upon the dates of data collection. Participants viewing the PSA will complete a brief pre-stimulus questionnaire. Once completed, respondents will view a brief (30-60 seconds) PSA addressing key points displayed in the *90 DAYS* narrative. At the conclusion of viewing the PSA, participants will complete a brief post-test questionnaire. If assigned to the control condition, participants will only complete the brief post-test questionnaire. All participants in the manipulation check will be compensated \$25 for their participation in the manipulation check.

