The third recruitment strategy consists of using a Qualtrics panel. According to Qualtrics, "A market research panel, also known as an online sample, is a group of people recruited to respond to a survey. They are typically chosen from a prearranged pool of respondents who've agreed to be contacted by a market research service in order to respond to surveys." Employing the study inclusion/exclusion criteria, Qualtrics panel, recruits willing participants for study participation. Participants recruited via the Qualtrics panel will be compensated directly via Qualtrics. They will receive a \$50 gift card for their participation.

Across all forms of recruitment, study conditions will be randomly assigned via the Qualtrics system. Once a participant provides consent and is screened for study inclusion, participants will complete the pre-test questionnaire. After completing the pre-test questionnaire, respondents will be assigned to one of two study conditions. They will either be asked to view one of the following: a brochure on safe disclosure or the 90 DAYS film. Upon completing one of the interventions, participants will be asked to immediately complete the post-test questionnaire. For participants recruited outside of the Qualtrics Panel, once all anonymous responses are submitted, they will be directed to a separate link to enter their randomized generated code and email address. The purpose of the randomized code is to verify that the participant completed the study. The purpose of the email address for those currently enrolled is two-fold. Firstly, it will allow researchers to compensate participants with a virtual \$30 Amazon gift card. Secondly, it will allow researchers to provide a follow up email, within 3-4 weeks, containing the link to the second

Version 10.5.2018 Page 4 of 11

post-test survey. Participants will be compensated with a \$20 virtual Amazon gift card. Altogether, currently enrolled respondents in the main study (N = 3), will receive a total of \$50 for their participation in the study. After each data collection, participants will be reminded of their right to withdraw their responses from the study without penalty.

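### The primary ANCOVA adjusts only for age and gives the pre-randomisation pre-test no role; if the outcome scales are on that pre-test, precision is given up at almost no cost

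*SAP*

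**What the plan says.** The Statistical Methods section of the SAP gives one model for internalized stigma, disclosure intentions and adherence intentions: "An Analysis of Covariance (ANCOVA) will be used to control for the influence of age on the relationships of interest". It names no other covariate, no change score and no repeated-measures term. The only analysis statement in the available protocol text is the choice of software, in section 7.

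The SAP's Study Overview shows that a baseline measurement exists: "Once consented, all participants completed a pre-test survey". It also gives the order: "Upon completing the pre-test, using the randomization feature in Qualtrics, participants were randomly assigned to one of two study arms". Protocol section 5 agrees: "After completing the pre-test questionnaire, respondents will be assigned to one of two study conditions". The same section describes the design as "a randomized clinical trial (RCT) with a pre and post questionnaire assessing two conditions".

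The hypotheses are worded as levels: "Participants in the EE condition will report: a) lower levels of internalized stigma; b) higher levels of disclosure intentions".

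Neither document lists the items on the main-study pre-test. Protocol section 5 does list "intimate partner disclosure intentions, medical adherence intentions, disclosure behavior, adherence behavior and reported internalized stigma", but as content of the second post-test, which applies only to the three women already enrolled. It also refers to a measures guide that is not among the documents.

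**The concern.** In a randomised comparison the main use of a covariate is to remove outcome variance. The plan accepts adjustment by choosing ANCOVA, but spends it on age alone. The obvious candidate is the same scale measured in the same woman shortly before she sees the film or brochure. It is taken before assignment, so the film cannot have affected it, and adjusting for it is legitimate.

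For any outcome scale that is on the pre-test, leaving it out gives a wider confidence interval and lower power than the same women could provide. Protocol section 5 stresses how difficult this population is to recruit, so information already collected is worth using.

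**Working it through.** **Inputs from the documents.** Age is the only covariate (SAP, Statistical Methods). The pre-test is completed by everyone before assignment (SAP, Study Overview; protocol section 5). The main study enrols up to 400 (protocol section 16), which is a ceiling and not a power-based target. There is no stated power, effect size, SD or alpha, so there is no figure of the plan's own to reproduce.

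**Assumptions.** The scale is on the pre-test; the dependent variable is the post-test score (SD 1); allocation is 1:1; the test is two-sided at 0.05; there is no dropout before the immediate post-test. The pre-post correlation is r = 0.3, 0.5 or 0.7. The correlation of age with both scores is a = 0 (case A) or a = 0.3 (case B).

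**Formulas.** The comparator is the planned age-adjusted model, so what counts is the pre-post correlation given age:

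- p = (r − a²)/(1 − a²)
- variance of the film effect, age-only over age plus pre-test = 1/(1 − p²)
- reduction in interval width = 1 − √(1 − p²)
- number of women giving the precision of 400 under the age-only model = 400(1 − p²)
- residual SD: √(1 − a²) for age-only, √((1 − a²)(1 − p²)) with the pre-test
- detectable effect and power: noncentral t on 2n − 2 − k degrees of freedom, with n women per arm and k covariates

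Example, case B with r = 0.5: p = (0.5 − 0.09)/0.91 = 0.451; variance ratio = 1/(1 − 0.203) = 1.25; equivalent total = 400 × 0.797 = 319.

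**Results, 200 per arm.** Age-only detectable effect at 80% power is 0.281 SD in A and 0.268 SD in B. Age-only power for a 0.2 SD effect is 51% in A and 55% in B.

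| Case | r | p | Variance ratio | Interval narrower by | Detectable effect with pre-test (SD) | Power at 0.2 SD with pre-test | Women needed to match 400 |
|---|---|---|---|---|---|---|---|
| A | 0.3 | 0.300 | 1.10 | 5% | 0.268 | 55% | 364 |
| A | 0.5 | 0.500 | 1.33 | 13% | 0.243 | 64% | 300 |
| A | 0.7 | 0.700 | 1.96 | 29% | 0.201 | 80% | 204 |
| B | 0.3 | 0.231 | 1.06 | 3% | 0.261 | 58% | 379 |
| B | 0.5 | 0.451 | 1.25 | 11% | 0.239 | 65% | 319 |
| B | 0.7 | 0.670 | 1.82 | 26% | 0.199 | 81% | 220 |

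**If only 100 per arm are enrolled**, the detectable effect falls from 0.398 to 0.380, 0.345 and 0.284 SD in A, and from 0.380 to 0.370, 0.339 and 0.282 SD in B.

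**Simulation check.** With 4,000 trials per cell at 200 per arm and a true effect of 0.2 SD, both models gave mean estimates of 0.198 to 0.201. Under no effect, type I error was 4.4% to 5.1%. Simulated variance ratios were 1.10, 1.33 and 1.99 in A, and 1.06, 1.25 and 1.81 in B, in line with the formulas.

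**Downside.** If the pre-test score is unrelated to the outcome, the cost is one degree of freedom: about 0.25% more variance with 400 women and about 1% with 100. In a separate simulation of that case with 400 women, the SD of the estimate was 0.1006 with the pre-test and 0.1004 without.

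**The case against.** **The deciding fact is not documented.** Nothing says that the three scales are on the pre-test, and the measures guide is cited only in connection with screening questions. This stands, and it is why the conclusion is conditional. A pre/post questionnaire design makes it likely that the scales are there, but does not establish it.

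**The dependent variable might be a change score.** The SAP does not say in so many words that the post-test score is analysed, and Aim 1 is phrased as decreasing stigma and increasing intentions. The hypotheses speak of levels, so the post-test score is the more natural reading. On the change-score reading, with age unrelated to the scores, the residual variance is 2(1 − r) against 1 − r² for pre-test-adjusted ANCOVA. The ratio is 2/(1 + r): 1.54, 1.33 and 1.18 at r = 0.3, 0.5 and 0.7. The gain then shrinks as r rises, so the table above does not apply, but adding the pre-test score still improves precision at each of these values.

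**The plan is valid as it is.** True: there is no bias, no inflation of type I error, and no stated precision target that is missed. At r = 0.3 the interval narrows by only 3% to 5%. This limits how serious the point is. It does not remove the case for a nearly free improvement.

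**It may be too late.** The Study Overview is in the past tense ("This randomized controlled trial was conducted among Black women living with HIV in the Southern U.S"), while the Data Collection Plan and Statistical Methods use the future. The documents do not settle whether arm comparisons had been seen, so the fix has to cover both possibilities.

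**No missing pre-test problem is described.** Also true. The missing-score rule proposed below is a precaution against losing women with an incomplete scale, not a response to a known defect.

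**Conclusion.** The concern holds, as a matter of efficiency and on the condition that the scale is on the pre-test. Age is the only covariate named, the pre-test precedes randomisation for everyone, and the analysis does not use it. On the post-test reading with 200 per arm, the age-only variance is 1.06 to 1.10 times larger than necessary at r = 0.3, 1.25 to 1.33 times at 0.5, and 1.82 to 1.96 times at 0.7. The gain is minor at the low end and close to a doubling of information at the high end. Pre-test, stimulus and post-test follow one another directly, so a weak correlation is not the natural expectation, but the documents give no figure. The point should be fixed, but it does not threaten the validity of the planned comparison. Confidence is medium, because the pre-test content and the correlation are both undocumented.

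**What to change.** 1. Confirm from the measures guide which of the three outcome scales are on the pre-test, and state in the SAP that the dependent variable is the post-test score.
2. For each scale that is on the pre-test, specify in the SAP:

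> The post-test score will be compared between arms by ANCOVA with the pre-test score of that outcome and age as covariates. A missing pre-test score will be replaced by the mean over both arms combined, so that no randomised woman is dropped for it.

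3. Report the age-only model as a sensitivity analysis. Keep it as the main model for any scale that is not on the pre-test.
4. Date the change and record whether arm comparisons had been seen. If they had not, the pre-test-adjusted model becomes primary. If they had, the age-only model stays primary and the adjusted model is reported as a labelled post hoc analysis, so that the choice of model cannot follow the result.

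The cost is a check of the questionnaire, a few dated sentences in the SAP and one degree of freedom per outcome. For scales on the pre-test no new data are needed, and SPSS fits the model.

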Due to the sensitive and hard to reach nature of this study population, multiple recruitment strategies will be implemented. Firstly, a two-step recruitment process will be employed. Based upon the inclusion and exclusion criteria, clinic staff throughout the Jackson Health System as well as other HIV service providers across the state of Florida, will inform patients of the study via print and virtual flyers, sent via email. Dependent upon the study schedule, research team members maybe stationed at recruitment sites to speak with interested patients who desire further information. If research staff are not onsite, interested participants can contact the identified study team member listed on the recruitment flyer should they have further questions. All virtual flyers will be sent by clinic staff via a restricted email server to patients who have agreed to be contacted via email by their health provider. For patients who receive a printed or virtual copy of the study flyer, if they are interested in participating, they will visit the Qualtrics link provided on the flyer. Once they are on the study site, participants will read the consent form which thoroughly outlines the study's purpose, inclusion criteria, risks, benefits, compensation, voluntariness, and researchers' contact information. Should participants decide the study is a good fit for them, they will be able asked to consent by clicking the "next" button. Upon clicking the "next" button participants will be asked screening questions based upon the study's inclusion criteria (See updated measures guide). Once screened, if participants meet the eligibility requirements they will be guided through the study. Should participants not meet the eligibility criteria, they will be redirected to the end of the study and thanked for their time. Participants will be fully aware via the consent form that they can withdraw from the study at any time.

The second recruitment method will consist of paid targeted Facebook advertising. This recruitment strategy has yielded successful results in similar populations as the

Version 10.5.2018 Page 3 of 11

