18) Provisions to Protect the Privacy Interests of Subjects

Only authorized members of the study team will have access to the data. Lastly, an assigned research team member will contact participants to provide a reminder of the follow up survey. Participants will be individually contacted and compensated via email.

19) Consent Process

The consent process for the PSA pre-test will be as follows. Firstly, clinic providers and staff will inform patients of the study, including the purpose of the study and participation criteria. Second, patients who express interest in participating will be provided contact information for a research team member who will be able to provide further information on the study. Due to the sensitive nature of this study, should a patient decline to participate, they will not be referred to the research team. The study team member will provide the interested participant with the consent forms to read and ask any questions to their full satisfaction and understanding. After the consent forms are signed and copies given to the participant, the study team member will administer the pre-questionnaire.

Version 10.5.2018 Page 8 of 11

Due to the main study being conducted via the Qualtrics survey software, participants will be provided a thorough consent form. Should the participant agree to participate, their consent will be determined based upon their decision to select "next" and complete the study. Moreover, all participants for the PSA manipulation check and main study will be informed of their right to remove themselves from the study or withdraw their responses at any time without penalty. Respondents will also have the contact information of the study team in case they have questions.

20) Process to Document Consent in Writing

For both the PSA manipulation check and the main study, participants will document their consent by completing the study questionnaires. Therefore, while informed consent will transpire, signed consent will not. This will reduce the amount of personal identifiable information reported.

Version 10.5.2018 Page 9 of 11

References

- AIDSVu. (n.d.) Miami (Miami-Dade County) Highlights. Retrieved from: https://aidsvu.org/state/florida/miami/
- Centers for Disease Control and Prevention. (2017). *Living with HIV*. Retrieved from: https://www.cdc.gov/hiv/basics/livingwithhiv/index.html

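### Does the SAP need to say whether women who skip or abandon the assigned film or brochure stay in the primary ANCOVA?

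*SAP*

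**What the plan says.** The SAP's Study Overview sets the order of events. Women complete the pre-test and are then allocated: "Upon completing the pre-test, using the randomization feature in Qualtrics, participants were randomly assigned to one of two study arms". Next comes the stimulus and the outcome: "After viewing the EE stimulus or the brochure, participants immediately completed a post-test survey". Protocol section 5 gives the same order and puts the main study online in Qualtrics.

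The Statistical Methods section is short. It says "An Analysis of Covariance (ANCOVA) will be used to control for the influence of age on the relationships of interest", and then states the comparison: "This analysis will determine if there is a statistically significant difference between the treatment arm (90 DAYS film) and the control arm (Brochure". The three primary variables are internalised stigma, intentions to disclose and intentions for medical adherence. The section does not mention an analysis set, intention-to-treat or per-protocol, a viewing criterion, or missing post-tests.

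Protocol section 5 allows women to leave: "Participants will be fully aware via the consent form that they can withdraw from the study at any time". Sections 5 and 19 also let them withdraw the responses they have given. On consent, section 5 says "they will be able asked to consent by clicking the" next button, while section 20 says "participants will document their consent by completing the study questionnaires". Screening items are in a separate document: "participants will be asked screening questions based upon the study's inclusion criteria (See updated measures guide". That guide is not among the documents, so whether viewing was recorded cannot be known from them.

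**The concern.** Two groups can form after randomisation in an unsupervised online trial: women who click past the film or brochure and still answer the post-test, and women who close the survey before the post-test. The SAP's account of conduct describes only women who viewed and completed, so a reader could take the analysis to be limited to viewers. Another reader could take *arm* to mean everyone allocated. With no stated rule, the choice could be made after the data are seen.

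If women who do not view would have scored worse anyway, removing them from one arm makes the arms differ for reasons other than the film. Adjustment for age alone would not repair a resulting imbalance in pre-test stigma or intentions. All three primary outcomes would be affected.

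**Working it through.** **Reading the text.** The plan states no figure to reproduce, so the first check is what the words commit to.

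1. Study Overview: the two arms are the groups formed by the Qualtrics randomiser.
2. Statistical Methods: the ANCOVA compares the treatment arm with the control arm. No other definition of arm appears.
3. Neither document has a viewing threshold, a per-protocol set or an exclusion after assignment. The completion code in Protocol section 5 belongs to the compensation step and is not an analysis criterion.
4. A woman with a post-test therefore enters the ANCOVA in her allocated arm, whether or not she viewed. A woman without a post-test has no outcome to enter, so the default is an analysis of those with post-tests.

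**Size if analysts departed from that reading.** Protocol section 16 gives a ceiling of 400 for the main study. Everything else is assumed: 200 per arm, SD 1, two-sided 5% test, no covariate adjustment, an effect of 0.3 SD in viewers, and non-viewing in the film arm only. Let *m* be the non-viewing share and *D* the amount by which non-viewers' outcomes would be worse anyway.

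- Kept as assigned: estimate = 0.3(1 − m), taking D = 0 for power.
- Removed: estimate = 0.3 + mD. With no true effect the bias is mD, with standard error √(1/200 + 1/[200(1 − m)]).

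| m | Kept: estimate, power | Removed, D = 0: estimate, power | Removed, D = 0.5: estimate | Type I error, D = 0.25 | Type I error, D = 0.5 |
|---|---|---|---|---|---|
| 5% | 0.285, 81.1% | 0.30, 84.0% | 0.325 | 5.2% | 5.7% |
| 10% | 0.27, 76.8% | 0.30, 83.0% | 0.35 | 5.7% | 7.7% |
| 20% | 0.24, 66.8% | 0.30, 80.5% | 0.40 | 7.6% | 15.6% |

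Power and error use the noncentral t distribution. For the bottom-right cell, bias = 0.20 × 0.5 = 0.10, standard error = √(1/200 + 1/160) = 0.106, ratio 0.94, which gives 15.6%. A simulation of that case (20,000 runs) gave 16.1% with removal and 5.1% when all were kept. At 100 per arm with D = 0.5 the errors are 5.3%, 6.4% and 10.2%.

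**Letting brochure readers skip too.** The table sets brochure non-viewing to zero. If brochure non-viewers with the same D = 0.5 are also removed, the bias is 0.5 × (m_film − m_brochure):

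- 20% against 10%: 0.5 × 0.10 = 0.05 SD, 160 against 180 women, type I error 7.4%.
- 20% against 15%: 0.5 × 0.05 = 0.025 SD, 160 against 170 women, standard error √(1/160 + 1/170) = 0.110, ratio 0.23, type I error about 5.6%.
- Equal shares of similar women: the bias cancels.

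The same arithmetic covers women who leave before the post-test. Loss of 20% against 10% again gives 0.05 SD and 7.4%, and heavier brochure loss reverses the sign.

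**The case for a change.** The best case for a change is that the omission is certain and the cost is small. The SAP gives no analysis set, it was dated after it describes the trial as conducted, and a sentence would close off a choice made with the data in view. It speaks of both efficacy and effectiveness, so the aim alone does not settle who should be analysed. Even a firm as-assigned reading says nothing about women with no post-test.

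Part of this stands. The silence on missing post-tests is real, and selective, unequal loss could bias the result without anyone choosing to exclude women. But a stated rule would not recover those outcomes. A sensitivity analysis that shifts missing film-arm scores by 0 to 0.5 SD would leave the primary result as it is. It would also need a direction for each outcome, a base imputation and a treatment of missing brochure scores before it meant anything.

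Two strands do not stand. The consent wording does not decide who enters the ANCOVA: the SAP places consent before the pre-test, and a woman who leaves after assignment has already completed one questionnaire. Age-only adjustment is a separate covariate question. A rule keeping every randomised woman with a post-test would also need an exception for those who withdraw their responses, which Protocol sections 5 and 19 allow.

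**Conclusion.** The concern identifies missing detail, not a flaw in the design or analysis. As written, the plan compares randomised arms and tells no one to drop non-viewers. Stating that explicitly would write down what is already implied. Participant numbers by arm and any record of viewing belong in the report of results.

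The larger bias figures require removal that the plan does not call for. The 15.6% error also needs 20% non-viewing in the film arm, none in the brochure arm, a 0.5 SD worse outcome among those removed, and enrolment at the 400 ceiling split equally. At 5% non-viewing the inflation is negligible, at 5.2% to 5.7%. Keeping everyone as assigned has a power cost (66.8% against 80.5% at 20% non-viewing and 0.3 SD), which is a fair price for a comparison protected by randomisation.

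The conclusion rests on reading *arm* as the randomised group. It would weaken if the measures guide, or the eventual report, showed that women were excluded for not viewing, or that losses before the post-test differed markedly between arms.
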